- Demonstrate that the delivery of the intervention(s) and the control intervention(s) under study can be delivered consistently, as defined by:
  - 85% or more of randomized participants engage in 1 or more sessions
  - 75% or more of randomized participants engage in at least 6 of 9 sessions
- Demonstrate the safety and tolerability of the intervention(s) used in the study by:
  - 5% or less of randomized participants experience a severe or serious adverse event related to the intervention(s)
  - 75% or more of randomized participants attend at least 6 of 9 sessions
  - 75% or more of randomized participants are satisfied with assigned program
- Demonstrate the fidelity of the intervention(s) used in the study by:
  - Program facilitators deliver 90% of session activities 90% of the time
- Demonstrate the ability to collect study data by:
  - 80% or more of randomized participants complete follow up at 2 months (end of the R61 study)
- Prior to submission of the written R33 transition request, submit R33 clinical study protocols and Data and Safety Monitoring Plan to NCCIH for review and approval
  - Submit the R33 clinical DSMP and SARP by the end of month 20
  - Submit a written R33 Transition Request by the end of month 21

All the above milestones must be reached before requesting transition to the R33 phase.

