#### 9.4.5 RETENTION STRATEGIES

There are many well-recognized barriers to research participation overall including inconvenience, time commitment, geographic location, etc. The investigators have decades of experience successfully addressing these challenges. We will implement the following strategies used in previous studies to facilitate study participant engagement in the interventions and data collection:

- Research staff will routinely track all study visits/time points per participant (screening and intervention session, follow-up) and will work closely with the Community Facilitators and Community Coordinators to devise timely solutions for mitigating retention issues.
- We will offer a range of program session times to accommodate participants' needs; this includes early mornings, day, and evenings. Saturday appointments are also an option, as needed. Programs will be offered in different formats (in-person, videoconference) with our host Community Partner Organizations to accommodate participant preferences and needs.
- If participants need to miss a program session, they will be able to view intervention session educational and skill videos by accessing the study website.
- All participants will be provided reminders of their study related visits.
- Participants will be provided detailed instructions on how to find Community Partner Organization sites for in-person visits; transportation instructions including bus, train, and

interstate routes will be included. Free, easily accessible parking will be made available to study participants.

- Transportation services to and from study visits will be provided to participants, as needed, using Transportation Plus, a Twin Cities based company. The study team will arrange taxi services for the participant. Prior to initiating the ride, participants will provide verbal consent to have their contact information (e.g., name, address, phone number) shared with Transportation Plus. Verbal consent will be captured in the study record. Transportation is paid for by the study; participants will not incur out of pocket costs.
- Participants will receive regular reminders (automated via text, email, or other methods depending on participant preference) to complete self-report questionnaires (SRQs). Study staff will closely monitor completion and contact participants if not completed within designated time frames.

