### 10.3 RANDOMIZATION & BLINDING

Eligible individuals will be enrolled and randomized using blocked randomization (with varying block sizes) following stratification for session offerings (e.g., Summer 2023 - Saturday mornings). Computer generated random treatment assignments will be prepared by the independent study statistician and conveyed electronically through REDCap (the electronic study database) at the time of enrollment to preserve allocation concealment. All study staff responsible for screening and enrollment procedures will be blinded to upcoming treatment assignments. The Co-PIs, select Co-Investigators, and the study statistician will be blinded until the study database is locked for analysis. The Co-PIs are authorized to be unblinded when needed for safety-related processes (e.g., decisions to withdraw participants from the intervention following adverse events).

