Procedures	Facilitator-led group sessions; includes viewing of expert-narrated videos specific to each intervention's content, workbook reflection activities, and facilitator-led group discussions  Participants are encouraged to practice in between sessions using the provided intervention-specific resources (e.g., workbooks, videos, etc.).
Delivery Format	Sessions offered in-person, via videoconference, or hybrid depending on community partner organization and participant needs. Group sessions with 7-16 participants per group
Location	See participating locations listed in section 4.3
Timing, Schedule	One session per week for 9 weeks 90 minutes per session Similar to other educational programs offered in community partner organizations.
Tailoring	Participants will be encouraged to practice at home, focusing on intervention specific content that meets their needs
Fidelity	10% of the interventions will be monitored by study investigators, either in-person or remotely using a fidelity checklist which will assess completion of required session activities; review of weekly session facilitator documentation in REDCap regarding ability to deliver session activities as planned, including rationale for activities not completed

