### 15.2.2 R33 RANDOMIZED HYBRID EFFECTIVENESS-IMPLEMENTATION TRIAL

Our sample size for the R33 Randomized Hybrid Effectiveness-Implementation Trial is based on findings from the literature on the PEG instrument (our primary outcome measure), including data on responsiveness and variability. We want at least 80% power to detect a group difference of approximately one unit or 10 percentage points on the PEG (0-10 scale) based on the mean of the 2, 4, and 6 month measures. We conducted simulation studies mimicking the structure of our planned study to assess the impact of sample size and group treatment factors (class size and number of classes) on power and detectable group difference. We used data on back pain intensity from the active control intervention (Keys to Wellbeing) in our team's recent trial of physical activity in older adults (R33AT00911) to inform intra-class correlation. We generated normally distributed longitudinal measurements from the 0-10 PEG scale with a moderate intra-individual correlation of 0.25, an intra-class correlation of 0.05, and a residual standard error of 2.5 units. The mean response was a function of normally distributed individual- and class-level random effects (with variances chosen to achieve the above correlations) as well as a constant fixed effect of treatment at the 2-, 4-, and 6-month time points. The mean PEG during follow-up was compared between treatment groups using a linear mixed model with fixed effects for treatment and baseline PEG and random effects for individual and class. We carried out simulations across a number of scenarios with class sizes ranging from 10 to 16 participants and a total sample size of 300. In all scenarios, our planned sample size yielded greater than

80% power for a treatment effect of approximately 0.9 units (0-10 scale), corresponding to a standardized between group effect size (mean difference/SD) of 0.36, which we regard as a clinically meaningful difference for pain intensity and interference, and is consistent with recommendations in the literature. To account for up to 20% loss to follow up, we plan to enroll a total of 376 participants.

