### 15.3 POPULATIONS FOR ANALYSES & GENERAL APPROACH (R33)

The primary analysis for the R33 Randomized Hybrid Effectiveness-Implementation Trial will use an intent-to-treat (ITT) approach with all enrolled subjects included in the analysis. Per-protocol analysis including only participants compliant with study protocols will be conducted as a secondary analysis. Secondary analyses are exploratory and will not be corrected for multiple comparisons. We will use hierarchical linear mixed model regression analyses to account for repeated measures within trial participants (the unit of randomization) in addition to the clustering of individuals within classes when receiving the experimental or control interventions. Missing data analyses will be informed by the pattern and reasons for missing data and will include multiple imputation (data missing at random) and sensitivity analyses using pattern mixture models (data not missing at random), if appropriate. This approach has been applied in previous trials by the investigators and highlighted as an exemplar in Annals of Internal Medicine.

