#### 15.4.2 R33 RANDOMIZED HYBRID EFFECTIVENESS-IMPLEMENTATION TRIAL

##### Primary Analysis

For the primary analysis, we will use mean PEG during follow-up (at 2, 4, and 6 months) as the outcome. The effect of treatment will be assessed using a hierarchical linear mixed model with fixed effects for treatment and baseline PEG and random effects for individual and class. In addition, we will test for evidence of an interaction between time and treatment by fitting a mixed model with an interaction between the treatment group indicator and follow-up time (viewed as a categorical random variable) and using a likelihood ratio test to assess whether the interaction terms are jointly significant. The results of this analysis will inform the interpretation of the primary analysis and guide secondary analyses. Analyses will be carried out using the statistical software R.

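### The primary model omits session offering, the randomisation stratum, so the treatment standard error is too large if offerings differ after baseline PEG adjustment

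*Combined protocol and SAP*

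**What the plan says.** - **Randomisation (Section 10.3).** Allocation uses "blocked randomization (with varying block sizes) following stratification for session offerings". The example given combines a season with a weekly time slot.
- **Primary analysis (Section 15.4.2).** The outcome is defined by "we will use mean PEG during follow-up (at 2, 4, and 6 months) as the outcome". The model has "fixed effects for treatment and baseline PEG and random effects for individual and class". No reference distribution or degrees of freedom (df) is named for the treatment test.
- **General approach (Section 15.3).** The mixed models handle repeated measures "in addition to the clustering of individuals within classes when receiving the experimental or control interventions". Offering is not mentioned.
- **Sample size (Section 15.2.2).** The power simulation fitted the same terms, with "class sizes ranging from 10 to 16 participants and a total sample size of 300", and generated only individual and class random effects.
- **Delivery (Section 11.1, Table 5, and Section 9.4.5).** Table 5 allows "Group sessions with 7-16 participants per group". On scheduling, the plan says "We will offer a range of program session times to accommodate" participants' needs.

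No section puts offering in the primary model or explains leaving it out.

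**The concern.** Each class belongs to one arm. If an offering runs at least one class per arm, its classes share whatever is common to that offering: season, time of day, format and the kind of person who chose it. Because randomisation is within offering, this shared level drops out of the difference between arms. The random class effect does not recognise that. It treats the shared level as independent variation between classes and carries it into the standard error of the treatment effect.

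Participants can choose times and formats that suit them, so offerings may well attract different people. Baseline PEG would remove part of such a difference, and only the remainder matters here. At stake is an interval for the primary effect that is wider than the randomisation warrants and, with class-level t df, a conservative test.

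**Working it through.** **Inputs from Section 15.2.2.** SD 2.5, intra-individual correlation 0.25, intra-class correlation (ICC) 0.05, effect 0.9 units, 300 analysed, classes of 10 to 16.

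**Assumptions not in the documents.** Two-sided 5% test, 1:1 allocation, equal class sizes, one class per arm per offering, 2.5 as the total SD (0.9/2.5 = 0.36, the plan's standardised effect), and 0.25 including the class component.

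**Variance components.**
- Total: 2.5² = 6.25
- Class: 0.05 × 6.25 = 0.3125
- Person: 0.25 × 6.25 − 0.3125 = 1.25
- Residual: 0.75 × 6.25 = 4.6875
- Baseline slope: b = 1.25/5.9375 = 0.2105
- Person-level variance of the three-visit mean after baseline adjustment: v = 1.25 + 4.6875/3 − 1.25²/5.9375 = 2.549

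**The plan's own figures.** With m per class and 150/m classes per arm, SE² = 2(0.3125 + v/m)/(150/m). At m = 10, SE = 0.275. With a normal reference, power is 90.5%, 87.4%, 84.2% and 81.0% at m = 10, 12, 14 and 16, so the statement of more than 80% reproduces. Enrolment is 300/0.8 = 375, against 376 stated.

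**Standard error excess.** Let f be the share of the class variance that lies at offering level (unknown). Let g be the part of the offering variance left after baseline adjustment: g = 1 if the offering difference is absent from baseline PEG, and g = (1 − b)² = 0.623 if equally present there. These are taken as extremes.

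Excess = √[(0.3125(1−f) + g·f·0.3125 + v/m) / (0.3125(1−f) + v/m)] − 1

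At f = 0.5 and m = 10, the class-only SE is 0.275 (g = 1) or 0.260 (g = 0.623), against 0.234. At m = 16 it is 0.317 or 0.297, against 0.259.

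| Analysed per class | f = 0.25, absent / present at baseline | f = 0.5, absent / present |
|---|---|---|
| 5.6 | 5.5% / 3.5% | 12.1% / 7.7% |
| 10 | 7.7% / 4.9% | 17.5% / 11.2% |
| 12.8 | 8.6% / 5.5% | 20.0% / 12.9% |
| 16 | 9.5% / 6.0% | 22.3% / 14.4% |

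At f = 0 the excess is zero. The rows for 5.6 and 12.8 are Table 5's limits after 20% loss (7 × 0.8 and 16 × 0.8). The ratios are the same if 2.5 is read as the residual SD.

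**Type I error.** Simulation with 500,000 trials per scenario, balanced REML with variances held at or above zero, class sizes 6 to 16, both baseline cases. Held df means classes minus offerings minus 1.

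| Analysis | f = 0 | f = 0.25 | f = 0.5 |
|---|---|---|---|
| Class only, t with class df | 5.0% | 3.4-4.2% | 2.0-3.5% |
| Class only, Wald z | 5.5-6.8% | 4.3-5.4% | 2.9-4.0% |
| Offering intercept, held df | 5.3-5.5% | 4.7-5.1% | 4.1-4.6% |

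With a Wald z reference, the offering model's type I error at f = 0 is 6.7-9.4%.

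**Power for 0.9 units at f = 0.5** (class-only with t df, then offering intercept with held df).

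| Class size | Absent at baseline | Present at baseline |
|---|---|---|
| 10 | 92% to 95% | 94% to 95% |
| 12.5 | 87% to 92% | 90% to 93% |
| 16 | 78% to 85% | 82% to 86% |

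At f = 0.25 the gain is 1 to 3 points. At f = 0 the two are within about 1 point either way.

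**Check on individual-level data.** Fitting baseline PEG as a covariate (4,000 trials per scenario; 15 offerings of 2×10 and 9 of 2×16) gave an excess at f = 0.5 of 17.0-23.5% (absent) and 13.3% (present). At f = 0.25 it was 6.1-11.0% and 6.0-6.7%.

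**The case against.** The strongest reply is that the standard error excess overstates the gain, because the remedy halves the df. At class size 16 they fall from 16 to 8 (t quantile 2.120 to 2.306, +8.8%); at class size 10, from 28 to 14 (2.048 to 2.145, +4.7%). Net of this, the class-only interval is on average about 3-6% wider than the offering-model interval at f = 0.25 and about 8-14% wider at f = 0.5. In a single trial the offering model often gives the wider interval: 63-67% of trials at f = 0, 43-56% at f = 0.25 and 24-43% at f = 0.5. One reason is that the offering variance is often estimated at zero. This stands and should temper expectations. The power figures above already include the df cost.

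Second, nothing is lost against the plan. With total class variance fixed at the planned ICC, class-only power rises with f; at class size 16 it goes from 74% (f = 0) to 78-82% (f = 0.5). That is correct: the loss is efficiency the design could have delivered, not a failed promise.

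Third, f is unknown, one class per arm per offering is inferred, and the only example of an offering dates from the pilot. These points also stand, and make the finding conditional.

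Fourth, whether the class-only test is conservative depends on a reference distribution that the plan does not state. With Wald z it is near 5% at f = 0.25. The missing df rule is a gap in its own right, but adding offering makes it more pressing.

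None of this supplies a reason to leave the stratum out. With held df the worst case is close to neutral.

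**Conclusion.** The concern holds as a conditional point about precision. The primary model ignores the randomisation stratum. If offerings differ after baseline adjustment, the standard error for 300 analysed in classes of 10 to 16 is overstated by 4.9-9.5% when a quarter of the class variance lies at offering level, and by 11.2-22.3% when half does. Over Table 5's group sizes after 20% loss the ranges are 3.5-8.6% and 7.7-20.0%. If offerings do not differ, there is no overstatement.

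The treatment estimate is unbiased, and the stated power is unaffected because it was simulated under the same model. The sizes rest on the assumed offering share, one class per arm per offering and equal class sizes. The change is worth making; the trial is not invalid without it. Confidence is medium because the offering variance is unknown.

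**What to change.** In Section 15.4.2, add session offering to the primary model as a random intercept, with class nested within offering. In the same sentence, state that treatment is tested with Kenward-Roger or Satterthwaite df (name one), never above classes minus offerings minus 1. That number is known before unblinding. The two parts belong together, because the offering term with a Wald z test would inflate type I error. Bring Section 15.3 into line.

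Fixed offering effects are not advised: if offerings do not differ they cost 1 to 6 power points (68% against 74% at class size 16).

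The cost is one or two sentences and no new data, since offering is already recorded as the stratum. If offerings do not differ, there is no gain, type I error is 5.3-5.5%, and power changes by about 1 point or less. Section 6.1 requires the team to "submit R33 clinical study protocols and Data and Safety Monitoring Plan to NCCIH for review and approval" before requesting transition, so the change can go into that submission, before any R33 outcome data exist.

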##### Secondary Analyses

**Responder Analyses:** We will derive responder categories for our primary outcome of pain intensity and interference (PEG) at 2, 4, and 6 months corresponding to reductions from baseline of 30% (minimal improvement), 50% (moderate improvement), 75% and 100% (substantial improvement). Then, we will fit proportional odds models to assess the effect of treatment on the probability of falling into each of these categories. In addition, we will conduct cumulative responder analyses to assess the proportion of responders for all possible levels of pain intensity and interference reduction (0 to 100% reduction).

**Secondary Outcomes:** Secondary numerical outcome measures (e.g., self-efficacy, life satisfaction, physical functioning) will be analyzed similarly to the primary PEG outcome. Generalized linear mixed models will be used for binary and count outcomes.

**Longitudinal Analyses:** Systematic reviews and meta-analyses of interventions for chronic pain and chronic back pain commonly use short-, medium-, and long-term treatment effects for analysis. Therefore, in addition to the analyses of primary and secondary outcomes which provide a measure of cumulative burden over the six-month study period, we will conduct longitudinal analyses with time coded as a categorical variable to quantify group differences in primary and secondary outcomes at 2, 4, and 6 months. Differences in numerical outcomes will be assessed using linear mixed models as described above. Differences in categorical outcomes (e.g., Graded Chronic Pain Scale, health care use) will be assessed using multi-level mixed effects generalized linear models.

**Effect Heterogeneity Analyses:** While it remains important to estimate the overall (mean) effect of an intervention, analyses of intervention studies have increasingly focused on characterizing how population subgroups experience differential treatment effects. Here, we will employ modern statistical machine learning methods (including some co-developed by co-I [name]) to describe how disparity factors (i.e. race, ethnicity, income, wealth, education, health care access) interact to influence how responsive individuals are to treatment. These flexible methods combining matching techniques

with decision trees will allow us to carry out a formal statistical test for effect heterogeneity, and (in the presence of heterogeneity) also yield simple classification rules that partition the population according to their expected treatment effect. In previous work, we have successfully applied these techniques to randomized trials with fewer participants (n=180) than we will have in this study (n=376) so we anticipate that we will have an adequate sample size to achieve meaningful results. For these analyses, we will use a limited set of outcomes (e.g., PEG, self-efficacy) at 2, 4, and 6 months to characterize the treatment effect. All analyses are exploratory and will not be corrected for multiple comparisons.

**Mediation Analyses:** In addition to characterizing how treatment effects vary across individuals, we will also explore the potential mechanisms driving these treatment effects via mediation analysis. Specifically, we will apply established methods to characterize the proportion of treatment effect for changes in pain intensity and interference at months 4 and 6 that can be explained by changes in self-efficacy, interoceptive awareness, and domain-specific life satisfaction measured in prior months. Mediation models will be estimated using the *mediation* package in R. Further, we will apply decomposition methods to understand whether the relationship between treatment effects and self-efficacy/life satisfaction is driven by mediation, moderation, or moderated mediation.

**Comparisons to Back Pain Populations with Low Health Disparities:** To assess the impact of Partners4Pain on mitigating disparities in pain self-management, we will compare findings to results from studies assessing self-management programs for chronic back pain with low PEHD representation, including studies from the HEAL initiative. This includes studies by our team assessing the impact of self-management for chronic neck and back pain. We will assess the similarity of mean outcome levels at baseline, treatment effects, drivers of effect heterogeneity, and mediating variables. Where possible, we will combine individual-level data (from previous studies conducted by our team) to formally test differences across studies.

**Implementation and Disparity Mitigating Outcome Analyses:** Qualitative measures will be analyzed using methods described previously (see R61 Aims 1 & 2). Quantitative measures will be summarized and compared between treatment groups using two-sample t-tests (for continuous measures) and chi-square tests (for categorical measures). Exploratory analyses will employ regression and decision tree models to investigate the impact of disparity factors (i.e., race, ethnicity, income, wealth, education, health care access) on measures of program implementation.

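### The responder analysis asks for the treatment effect on each improvement category but names only a proportional-odds model, with no proportionality check or per-cutoff estimate.

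*Combined protocol and SAP*

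**What the plan says.** Section 15.4.2, Responder Analyses, derives categories at 2, 4 and 6 months from "reductions from baseline of 30% (minimal improvement), 50% (moderate improvement), 75% and 100% (substantial improvement"). Then, it states, "we will fit proportional odds models to assess the effect of treatment on the probability of falling into each of these categories". Nothing is said about testing proportionality, relaxing it, or modelling the cutoffs separately.

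The next sentence adds a companion: "we will conduct cumulative responder analyses to assess the proportion of responders for all possible levels of pain intensity and interference reduction". No model, test or interval is named for it.

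Two other statements matter here. Under Secondary Outcomes, the same section plans generalized linear mixed models for binary and count outcomes. Section 15.3 sets the status: "Secondary analyses are exploratory and will not be corrected for multiple comparisons".

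**The concern.** The question is posed category by category, with a clinical label on each. The model has a single treatment parameter. It does return a fitted probability for every category, but the treatment effect at each cutoff is imposed as equal to the others rather than estimated there. One p-value then serves the minimal, moderate and substantial levels alike.

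Most participants are likely to lie around the lower cutoffs, so the common odds ratio is driven mainly by what happens there. What is at stake is any statement about a particular level, above all substantial improvement, because that statement would rest partly on an assumption the plan does not say it will check.

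**Working it through.** **Inputs from the documents (Section 15.2.2).** Effect 0.9 PEG units, SD 2.5, 300 evaluable. The planning figures reproduce: 0.9/2.5 = 0.36 as stated, and 300/0.80 = 375, against 376 planned (the next even number). The documents give no figure for the responder analysis.

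**Assumptions, not in the documents.** 1:1 allocation (150 per arm), two-sided 5% level, one visit, no clustering. Controls have baseline PEG 6 and a normal follow-up score with mean 5 and SD 2.5.

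**Step 1: control rates.** A reduction of at least r from 6 means a score of 6(1 − r) or less, that is 4.2, 3.0, 1.5 and 0. The rates are Φ((c − 5)/2.5):
- 30%: Φ(−0.32) = 37.4%
- 50%: Φ(−0.80) = 21.2%
- 75%: Φ(−1.40) = 8.1%
- 100%: Φ(−2.00) = 2.3%

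**Step 2: the model.** logit P(reaching cutoff k or better) = αₖ + β × treatment. There are four intercepts and one β, so exp(β) is the odds ratio at all four cutoffs.

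**Step 3: four patterns of effect.**
- *Uniform*: every treated participant is 0.9 lower (mean 4.1), giving 51.6%, 33.0%, 14.9% and 5.1%.
- *Low only*: +15 and +12 points at 30% and 50%, nothing at 75% or 100%.
- *Top only*: +10 points at 75% or more, 5 of them also at 100%, nothing at 30% or 50%.
- *Uneven*: the same 0.9 mean effect given to 20% of treated participants (0.9/0.20 = 4.5 units each), others unchanged. The rate is 0.8 × Φ((c − 5)/2.5) + 0.2 × Φ((c − 0.5)/2.5). At the 75% cutoff, 0.8 × 0.081 + 0.2 × 0.655 = 19.6%.

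The common odds ratio is the maximum-likelihood proportional-odds fit to these proportions. Rejection rates are simulated, using the proportional-odds score test and a two-proportion test at the 75% cutoff.

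| Pattern | True OR at 30 / 50 / 75 / 100% | Common OR | True rates at ≥75%, control vs treated | Fitted rates at ≥75% | Model significant | 75% cutoff test significant |
|---|---|---|---|---|---|---|
| Uniform | 1.78 / 1.83 / 2.00 / 2.28 | 1.82 | 8.1% vs 14.9% | 8.5% vs 14.5% | 76% | 47% |
| Low only | 1.84 / 1.85 / 1 / 1 | 1.76 | 8.1% vs 8.1% | 6.0% vs 10.1% | 72% | 5% |
| Top only | 1 / 1 / 2.51 / 3.37 | 1.10 | 8.1% vs 18.1% | 12.6% vs 13.6% | 7% | 75% |
| Uneven | 1.58 / 1.90 / 2.77 / 4.90 | 1.78 | 8.1% vs 19.6% | not computed | not computed | not computed |

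With smaller low-cutoff gains (12 and 8 points) the model is significant in about 50% of trials.

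**Step 4: other control rates.** Control rates were varied from 30/18/7/2% to 50/35/18/6% at the four cutoffs.
- Low-only pattern: common OR 1.62 to 1.77, significant in about 60% to 72% of trials.
- Top-only pattern: common OR 1.06 to 1.21. Power is about 3% to 12%, against 55% to 85% for a direct comparison at 75%.

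**Step 5: the uniform case with varying baselines.** With a constant 0.9 shift, within-person correlation 0.25, mean baseline 5 to 7 and control improvement 0.5 to 1.5, the cutoff odds ratios are 1.76–1.79, 1.79–1.97, 1.90–2.32 and 2.07–2.77. All favour treatment and rise moderately, so a common value is a fair and somewhat conservative summary for the high cutoffs.

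**The case against.** A reader might infer that the plan will report a 30–50% gain as a 75–100% gain and will miss a gain confined to the top. The documents do not support that as a certain outcome. Both errors need a marked breach of proportionality, and the constant 0.9-unit effect in Section 15.2.2 does not produce one. Nor does the plan say that a significant common odds ratio will be read as proof of benefit at 75% or 100%.

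The sharpest contrasts are also hand-built. In the top-only pattern, the 50–74% band falls from 21.2 − 8.1 = 13.1% to 21.2 − 18.1 = 3.1% while nobody crosses the 30% or 50% cutoff, and no mechanism for this is offered. The small to moderate effects in Table 1 say nothing about where on the responder scale people move, so they do not make a low-cutoff pattern more likely. The cumulative responder analysis would place the observed proportions at 75% and 100% beside the model. The primary linear mixed model and the sample size are untouched.

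All of that stands and limits the weight of the point. Two things remain. The constant shift is a sample-size device, whereas Section 15.4.2 also plans a formal test for effect heterogeneity. If benefit is uneven between people, cutoff odds ratios can diverge at an unchanged mean effect, as the uneven pattern shows. And the cumulative analysis carries no named estimate or interval, so the common odds ratio would be the only named inferential result for the categories.

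**Conclusion.** The point holds in limited form. The stated aim is an effect on each category, and the only named model assumes that effect to be the same at every cutoff, with no check or fallback. If proportionality fails, the distortion at the 75% level can be material in either direction: a fitted gain of about 4 points where there is none, or a true odds ratio of 2.77 summarised as 1.78. If the effect is close to a uniform shift, the common odds ratio is a sound summary and has more power than separate tests.

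The sizes rest on assumed responder rates, 150 per arm, a two-sided 5% level, one visit and no clustering. The analysis is secondary and exploratory, so this affects how particular improvement levels are interpreted and not the trial's primary conclusion. It is a lower-priority improvement.

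**What to change.** In Section 15.4.2, Responder Analyses:
- Keep the proportional-odds odds ratio as the single overall summary.
- Add the Partners4Pain minus Keys to Wellbeing difference, with a 95% CI, at each stated cutoff (30%, 50%, 75%, 100%), from the generalized linear mixed models already planned for binary outcomes. If 100% reductions are sparse, give a descriptive count there.
- Base any statement about a particular improvement level on the estimate at that cutoff.

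The cost is a wording change and a few extra model fits, with no new data. The price is precision and multiplicity. Under the uniform 0.9 shift, separate tests have about 70%, 63%, 47% and 24% power at the four cutoffs, against 76% for the ordinal model, so intervals at 75% and 100% will be wide. Four cutoffs at three visits also make 4 × 3 = 12 uncorrected exploratory contrasts, which should be reported as estimates rather than as a list of tests.
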